nursing staff will be blinded to which group patients were assigned. The infusion bag will be dispensed by pharmacy based on the randomization protocol and labeled “Lidocaine Infusion Study” with the corresponding IRB number.

The anesthesiologists assigned to the case will begin with a bolus infusion of lidocaine, 1.5 mg/kg (max 100 mg of lidocaine) at the time of anesthesia induction, followed by a continuous infusion set at 1.5 mg/kg/hour from the IV bag labeled “Lidocaine Infusion Study”

Actual body weight will be utilized in the dosing of lidocaine with a limit of 100mg of lidocaine bolused and maximum infusion rate not to exceed 3mg/min. Patients with BMI >40 are excluded from the study.

Intraoperative opioids will be limited to fentanyl in order to standardize intraoperative opioid requirements and intraoperative ketamine will be avoided. The surgical team is instructed not to infiltrate the surgical wound with local anesthetic during or at the end of surgery. The lidocaine infusion will be continued in the PACU. The nurse in the PACU will be instructed to discontinue the infusion when the patient meets PACU discharge criteria. The nurse and the surgical team are instructed not to use fentanyl during the postoperative period for analgesia. Prior to the discontinuation of the infusion, every patient will have a lidocaine level drawn before leaving the PACU.

Intra-op and PACU *stopping* rules

- If unstable arrhythmias are noted in the OR/PACU, the infusion will be stopped and a plasma lidocaine level will be drawn.
- If symptomatic bradycardia and significant hypotension refractory to treatment, consider stopping the infusion.
- If significant intra-operative hemorrhage (1 body blood volume), consider stopping the infusion.
- If the patient requires ICU admission after surgery due to intraoperative complications, the infusion will be stopped at the end of surgery.
- If the patient in the PACU demonstrates sudden changes in mental status, convulsion, or coma, the infusion will be stopped and a lidocaine level will be drawn.
- If mortality or major complications were to occur during the study, the cases will be reviewed by the primary investigator and co-investigators to determine the cause and if poor outcome is related to the study. All such cases will also be reported to IRB.

Baseline Assessments

1. Pain at rest and with coughing via a Numerical Rating Scale (NRS) – completed on the day of surgery in preop holding area

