2. Quality of Recovery (QoR-15) questionnaire – completed at the time of consenting or preop on the day of surgery.

Assessment and management in the PACU (day of surgery)

1. Pain scores via a Numerical Rating Scale (NRS) will be assessed in the PACU at rest and with coughing at the time of PACU arrival and at 30 minute intervals (Appendix A). (15) If the

patient is too somnolent upon arrival in the PACU and unable to participate, then the findings are to be documented as such (i.e., unable to participate).

2. Upon arrival to PACU and at 30 minutes, patient's level of consciousness will be assessed via the Richmond Agitation-Sedation Scale (RASS) (Appendix B).
3. Upon arrival to PACU and at 30 minute intervals the patient will also be evaluated by the PONV Impact Score (Appendix C).
4. Fentanyl use will be avoided in the PACU.
5. Total opioid requirements in the PACU will be noted. Converted to morphine equivalents as per Table 1.
6. Use of ketorolac or acetaminophen will be noted
7. Incidence of nausea/vomiting and administered treatment in PACU will be noted.
8. PACU length of stay (defined as the time from PACU admission until discharge criteria are met as per PACU nurse evaluation and documentation).
9. At time of the patient meeting discharge criteria in the PACU, lidocaine infusion will be stopped and lidocaine plasma levels will be drawn in all patients in order to keep the PACU staff blinded.

Assessment of the patient on the floor

1. The patient will be assessed by floor nurse on POD #0 at 8 PM and POD #1 at 8 AM and 8PM.
2. Pain will be assessed via the NRS scale at the prescribed times at rest and with coughing. Nurses will also rate the patients' average pain on a scale from 0 to 10 (0=no pain; 10=worst pain ever experienced) in the past 12 hours, or since their time of surgery if it is POD #0.
3. The current level of consciousness will be evaluated using the RASS score.
4. At 24 hours from the time of arrival to PACU, the patient's quality of recovery will be evaluated by the one of the study coordinators via a validated 15-question Quality of Recovery (QoR – 15) questionnaire.
5. At 24 hours from the time of arrival to PACU, the score on PONV Impact Scale will be obtained.
6. Need for nasogastric (NG) tube during hospital stay will be noted.

Return of bowel function

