Sample Size – The study will include 50 patients to be randomized and blinded in two groups of 25 patients each. No prior studies have been conducted on patients undergoing pancreatectomies and receiving a lidocaine infusion. However, several studies have shown statistical significant improvement in postoperative pain control and reduction of opioid requirement with the use of lidocaine infusion for intraabdominal surgeries, and often requiring 20 to 50 patients. (8) Additional 7 subjects will be screened to reach target accrual of 50 patients.

Data Collection –

Preoperative

1. Age, Sex, ASA Physical Status, Height, Weight, and BMI
2. Analgesics including opioids, NSAIDs, and/or acetaminophen (as per home medication list)
3. Current pain score as per NRS scale
4. QoR - 15

Intraoperative

1. Total pancreatectomies or pancreatoduodenectomies (as per post-op surgical note)
2. Open or laparoscopic (note if the case was converted to open)
3. Surgeon 1 or 2 (Drs. [name] or [name])
4. Duration of surgery
5. Duration of lidocaine infusion (time from induction to discontinuation in the PACU)
6. Total amount of fentanyl used in the OR.
7. Amount of anesthetic gas used (sevoflurane at 2L/min of fresh gas flow)
 - i. At the conclusion of the surgery, the anesthetic gas consumption will be as recorded by our Apollo Anesthesia Machine – Dräger
 - ii. Hourly vapor anesthetic requirements will be determined by the total anesthetic gas used divided by duration of the case (intubation time to surgery end time)

PACU

1. Pain score on arrival to PACU and at 30 minutes at rest and with coughing using the NRS scale
2. RASS score on arrival to PACU and 30 minutes after PACU admission
3. Incidence of PONV as reported and treated by PACU nurse.
4. Opioid requirements as converted into morphine equivalents (Table 1)
5. Use of acetaminophen or NSAIDs
6. Total PACU time (arrival to PACU until meeting discharge criteria as per PACU nurse)
7. Time of the discontinuation of the infusion
8. Plasma lidocaine level at the discontinuation of the infusion

Table 1: Morphine-equivalent based on an opioid equianalgesic

Opioid Drug (mg)	Administered	equianalgesic ratio to oral morphine
Morphine	PO	1:1
Morphine	IV	3:1
Oxycodone	PO	1.5:1
Hydrocodone	PO	1:1
Fentanyl	IV	300:1
Fentanyl	Transdermal	70:1
Oxymorphone	PO	3:1
Oxymorphone	IV	30:1
Hydromorphone	IV	18:1
Hydromorphone	PO	4:1
Tramadol	PO	0.3:1

Postoperative day 0 -1

1. POD #0 at 8PM and POD #1 at 8AM and 8PM:

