 - a. Current pain via NRS scale at rest, coughing, and average of the past 12 hours or since surgery if POD #1
 - b. Current RASS score
2. At 24 hours from arrival to PACU
 - a. Quality of Recovery (QoR – 15) questionnaire with assistance of a co-investigator (16).
 - b. Opioid requirements as converted into morphine equivalents
 - c. Acetaminophen or NSAIDs use

Hospital stay

1. First time to flatus (in days)
2. First time to bowel movement (in days)
3. Presence of NG tube (in days)
4. Length of hospital stay (in days)

Outpatient follow up

1. QoR – 15 via telephone call

Data Handling – Data will be entered into a secure REDCap database by study assistant. Principal Investigator will verify data to ensure accuracy.

Data Analysis - A t-test will be used to analyze mean differences in NRS scores, opioids requirements, and return of bowel function between groups. Complication rates will be analyzed using a Chi-squared analysis.

Feasibility and Time Frame – About 100 pancreatectomies per year are done at our institution. Anticipating that 50% of patients are not enrolled due to the exclusion criteria or unwillingness to

participate in the study, the anticipated time frame of patient recruitment for this study will be one year.

Strengths – The study focuses on a patient population that frequently has difficulties with postoperative pain control, delayed return of bowel function and ileus, which are often exacerbated by opioids. This study will determine if incorporating lidocaine infusions will be of help to this patient population. Also, the proposed study has been previously performed on similar surgical procedures with demonstrating improved postoperative analgesia and without any adverse outcomes (8, 9, 10). All drugs and personnel required for this study are readily available and in place at Mayo Clinic.

Limitations – Even though highly unlikely, the potential for local anesthetic toxicity exists. During the patients' intraoperative course, EKG, blood pressure, and pulse oximeter will be closely monitored for any potential signs of arrhythmias. If there is any suspicion of local anesthetic toxicity, the infusion will immediately be discontinued, the anesthesiologist taking care of the patient will be unblinded, and a serum level of lidocaine will be drawn at that time if appropriate. Close monitoring of the patients will also continue to take place in the PACU, as is the standard of care.

5. Human Subjects

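### Floor pain is scored at three times per patient, but the plan names only a t-test, with no time point, per-patient summary or missing-score rule; a mixed model would use these data better

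*Combined protocol and SAP*

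**What the plan says.** Under Assessment of the patient on the floor (section 4): "The patient will be assessed by floor nurse on POD #0 at 8 PM and POD #1 at 8 AM and 8PM". And: "Pain will be assessed via the NRS scale at the prescribed times at rest and with coughing". The Data Collection list repeats these three times. Each patient can therefore contribute three floor scores at rest and three with coughing, plus a separate rating of average pain over the preceding period.

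The Data Analysis paragraph gives these scores one sentence: "A t-test will be used to analyze mean differences in NRS scores, opioids requirements, and return of bowel function between groups". Neither that paragraph nor any other part of the document names a time point, a per-patient summary, a repeated-measures method, a covariate or a rule for missing scores. Rest and cough pain are also recorded before surgery (Baseline Assessments), but the analysis does not use them.

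The Sample Size paragraph states: "The study will include 50 patients to be randomized and blinded in two groups of 25 patients each". The support given is precedent, namely that earlier studies found benefit, "and often requiring 20 to 50 patients". No effect size, standard deviation, significance level or power is stated.

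**The concern.** A two-sample t-test takes one value per patient. With three values available and no summary defined, the natural reading is a separate test at each time. Such a test ignores the patient's other two scores and leaves out anyone whose score at that time is missing, even if the other two were recorded.

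Analgesia is one of the two aims in Specific Aims, and 25 patients per arm gives an imprecise comparison. The repeat scores are collected anyway, so whatever precision they offer costs no extra patients or visits. The issue here is precision, use of partial data and clear specification, and not the number of tests performed.

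**Working it through.** **Inputs from the document.** 25 patients per arm; three floor times; a t-test.

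**Assumed, because the document gives no value.** Two-sided 5% level; equal variance at the three times; a common correlation ρ between any two times, shown from 0.3 to 0.9; for missing scores, an independent 10% or 20% chance at each time. Results are in SD units, so no NRS standard deviation is needed.

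**Step 1, the plan's own figure.** N = 50 cannot be reproduced, since no inputs are given. For reference, a t-test on one score with 25 per arm has 80% power at a difference of about 0.81 SD.

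**Step 2, one time against the three-time average, complete data.**
- One time: SE = √(2/25) = 0.283 SD.
- Average of three: SE = √[(2/25) × (1 + 2ρ)/3].
- SE ratio = √[(1 + 2ρ)/3]; equivalent sample size multiplier = 3/(1 + 2ρ).

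| ρ | SE of average (SD) | SE ratio | Equivalent increase in patients | Power, constant 0.6 SD effect (one time: 55%) |
|---|---|---|---|---|
| 0.3 | 0.207 | 0.73 | 88% | 81% |
| 0.5 | 0.231 | 0.82 | 50% | 72% |
| 0.7 | 0.253 | 0.89 | 25% | 64% |
| 0.9 | 0.273 | 0.97 | 7% | 58% |

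Power is from the noncentral t distribution with 48 degrees of freedom, using 0.6 divided by the SE ratio as the standardised effect.

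**Step 3, where the gain comes from.** In one simulated trial (ρ = 0.5, SD 2, complete data), a mixed model and a t-test on each patient's mean of three both gave an SE of 0.467 for the average. The model with arm-by-time terms and no covariate returned exactly the same difference at each time as the raw group means (-0.63, -1.66 and -1.20). With complete data and no covariate, the model does not sharpen a single-time estimate.

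**Step 4, missing scores.** At ρ = 0.5, the model's SE relative to a t-test at the last time is:

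| Missing per time | Last-time effect | Three-time average | Patients with all three scores | Patients with at least one |
|---|---|---|---|---|
| 0% | 1.00 | 0.82 | 100% | 100% |
| 10% | 0.98 | 0.79 | 0.9³ = 73% | 1 − 0.1³ = 99.9% |
| 20% | 0.97 | 0.76 | 0.8³ = 51% | 1 − 0.2³ = 99.2% |

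A t-test on patient means restricted to complete triples would keep 73% or 51% of patients. The model keeps nearly all.

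**Step 5, a fading effect.** Suppose the true effects are 0.8, 0.4 and 0.1 SD. Single-time power is 79%, 28% and 6%. The average effect is (0.8 + 0.4 + 0.1)/3 = 0.433 SD; dividing by the SE ratio gives 0.593, 0.531 and 0.484 at ρ = 0.3, 0.5 and 0.7, with power 54%, 45% and 39%. Under a milder fade (0.8, 0.6, 0.5 SD; average 0.633), power for the average is 85%, 77% and 69%, against 79% at the first time.

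**The case against.** The strongest reply has four parts.

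- **The gain is from averaging, not from the model.** This stands. Step 2 compares an average effect with a single-time effect, which are different quantities, and Step 3 shows that a t-test on patient means does as well with complete data. A reader might infer that a mixed model makes every pain estimate more precise. It does not: a per-time estimate improves only through partially missing scores or baseline adjustment.
- **The plan does not say that it tests one score at a time.** This also stands. A reader might infer that the trial is committed to discarding two of three scores. The text leaves open a per-patient summary; the documented gap is that nothing is specified. A summary would still need a rule for patients with one or two scores.
- **The average may be the wrong headline.** Under Intraoperative lidocaine infusion protocol, the infusion ends when PACU discharge criteria are met, so floor scores follow the end of treatment and a fade is plausible. Step 5 shows that the average can then have less power than the first evening alone. The document does not support making the average the only result.
- **Correlation and missing rate are assumed.** True. At ρ = 0.9 the gain is only 3%. The document's provision for patients who cannot give a score concerns PACU arrival, so it says nothing about how often floor scores will be missing.

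None of these defends the present wording, which leaves the time point, the summary and the handling of missing scores undecided.

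**Conclusion.** The point holds as an inexpensive improvement and should be made. Floor rest and cough pain has three scores per patient and an analysis that does not say how to use them. A mixed model keeps every patient with at least one floor score, gives up nothing of substance at each time, and adds an overall effect whose SE is 27% to 3% smaller than at one time for assumed correlations of 0.3 to 0.9. The value of baseline adjustment cannot be sized from the document.

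A reader might go further and infer that the planned t-tests are invalid or biased. The document does not support that: in a randomised comparison, a t-test at a stated time is a valid analysis. The loss is in precision, in patients with partial data and in clarity about the result to be reported. The size rests on equal variances and an assumed correlation. The missing-data benefit also rests on an assumed rate, and on missingness that the observed scores can account for.

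**What to change.** For the floor rest and cough scores only, replace the t-test in Data Analysis with text to this effect:

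- One linear mixed model for rest and one for cough, over the three floor times, with arm, time, arm-by-time and the preoperative NRS of the same type.
- Unstructured within-patient covariance (six parameters) and a small-sample degrees-of-freedom correction such as Kenward-Roger.
- Every patient with at least one floor score is included, with a stated rule for a missing baseline score so that the covariate does not remove patients.
- Report the arm difference at each time and the difference averaged over the three times, all with 95% CIs from the same model.
- State before unblinding which of these is the main floor pain result.

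PACU scores and the 12-hour average rating keep their own analysis, which the text should say so that they are not left without one.

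The cost is a short change to the analysis text and slightly more analysis work; visits, treatment and sample size are unchanged. The drawback is that an averaged result is diluted if benefit is confined to the first evening, which is why the per-time estimates must stay. If the team prefers to keep a t-test, the minimum is to name the time point or per-patient summary and give a rule for missing scores.

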Appendix A – Pain Assessed via the Numerical Rating Scale (NRS) (11)

The patient is asked to rate their current pain on a scale from 0 (no pain) to 10 (worst pain imaginable) at rest and with coughing.

Appendix B – Richmond Agitation-Sedation Scale (12)

Score	Classification	Description
4	Combative	Overly combative, violent, immediate danger to staff
3	Very agitated	Pulls or removes tube(s) or catheter(s); aggressive
2	Agitated	Frequent nonpurposeful movements; fights ventilator
1	Restless	Anxious but movements not aggressive or vigorous
0	Alert and Calm	
-1	Drowsy	Not fully alert, but has sustained awakening to voice (eye opening/eye contact >10 seconds)
-2	Light Sedation	Briefly awakens with eye contact to voice (< 10 seconds)
-3	Moderate Sedation	Movement or eye opening to voice but no eye contact
-4	Deep Sedation	No response to voice, but movement or eye opening to physical stimulation
-5	Unarousable	No response to voice or physical stimulation

Appendix C – The PONV Impact Scale (13)

Q1. Have you vomited or had dry-retching*?

- 0. No
- 1. Once
- 2. Twice
- 3. Three or more times

Q2. Have you experienced a feeling of nausea ("an *unsettled feeling in the stomach and slight urge to vomit*")? If yes, has your feeling of nausea interfered with activities of daily living, such as being able to get out of bed, being able to move about freely in bed, being able to walk normally, or eating and drinking?

- 0. Not at all
- 1. Sometimes
- 2. Often or most of the time
- 3. All of the time.

To calculate the PONV Impact Scale score, add the numerical responses to questions 1 and 2. A PONV Impact Scale score of ≥ 5 defines clinically important PONV.

**count distinct episodes: several vomits or retching events occurring over a short time frame, say 5 min, should be counted as one vomiting/dry-retching episode; multiple episodes require distinct time periods without vomiting/dry-retching.*

Appendix D – Quality of Recovery (QoR – 15) Questionnaire (14)

QoR-15 Patient Survey

Date: ___/___/___

Study #: _____

Preoperative

Postoperative

PART A

How have you been feeling in the last 24 hours?

(0 to 10, where: 0 = none of the time [poor] and 10 = all of the time [excellent])

1. Able to breathe easily	None of the time	0	1	2	3	4	5	6	7	8	9	10	All of the time
2. Been able to enjoy food	None of the time	0	1	2	3	4	5	6	7	8	9	10	All of the time
3. Feeling rested	None of the time	0	1	2	3	4	5	6	7	8	9	10	All of the time
4. Have had a good sleep	None of the time	0	1	2	3	4	5	6	7	8	9	10	All of the time
5. Able to look after personal toilet and hygiene unaided	None of the time	0	1	2	3	4	5	6	7	8	9	10	All of the time
6. Able to communicate with family or friends	None of the time	0	1	2	3	4	5	6	7	8	9	10	All of the time
7. Getting support from hospital doctors and nurses	None of the time	0	1	2	3	4	5	6	7	8	9	10	All of the time
8. Able to return to work or usual home activities	None of the time	0	1	2	3	4	5	6	7	8	9	10	All of the time
9. Feeling comfortable and in control	None of the time	0	1	2	3	4	5	6	7	8	9	10	All of the time
10. Having a feeling of general well-being	None of the time	0	1	2	3	4	5	6	7	8	9	10	All of the time

PART B

Have you had any of the following in the last 24 hours?

(10 to 0, where: 10 = none of the time [excellent] and 0 = all of the time [poor])

11. Moderate pain	None of the time	10	9	8	7	6	5	4	3	2	1	0	All of the time
12. Severe pain	None of the time	10	9	8	7	6	5	4	3	2	1	0	All of the time
13. Nausea or vomiting	None of the time	10	9	8	7	6	5	4	3	2	1	0	All of the time
14. Feeling worried or anxious	None of the time	10	9	8	7	6	5	4	3	2	1	0	All of the time
15. Feeling sad or depressed	None of the time	10	9	8	7	6	5	4	3	2	1	0	All of the time
